#### 1434 4.6.5. Statistical Analysis

1435 Initial analysis of HCC will be primarily descriptive. The characteristics of HCC patients 1436 described will include TNM explant pathologic stage, use of ablation pre-transplant, and 1437 pre transplant ablation method (i.e. chemoembolization, RFA, etc.). The proportion of 1438 HCC recurring within one year will be presented, with 95% CI. Predictors of one-year 1439 recurrence will be explored using logistic regression for patients with at least one year of 1440 follow-up. The difference between recurrence (or presence) proportions for LDLT versus 1441 non-LDLT patients will also be estimated using a 95% confidence interval. A comparison 1442 of survival between these two groups will be performed using Cox regression, adjusted 1443 for various prognostic covariates. A comparison of survival between LDLT and 1444 deceased donor transplant recipients will also be performed. 1445 Secondary outcomes include comparisons of numbers of ablative procedures for LDLT 1446 versus waiting for DDLT, and numbers of surgical complications for LDLT versus 1447 DDLT. Differences in numbers of ablative procedures will be analyzed using Poisson 1448 regression, assuming that multiple ablative procedures may be necessary for some 1449 patients. Differences in surgical complications will be analyzed using logistic regression,

- 1450 assuming each complication either does or does not occur for each patient in a given time 1451 frame
- 1452 1453

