#### **Potential Recipients Potential Donors** With Donor H&P No Donor H&P Primary Brief No LDLT Contemporaneous Donor Actual LDLT DDLT or DDLT Aims Description DDLT (as needed) Donors Controls LDLT vs. 1 Х Х Х non-LDLT LDLT vs. 2 Х Х Х DDLT Х Х 3 QOL Х Х Х Informed 4 Х Х Consent Secondary Aims Hepatitis C 1 Х Х Х (at transplant) HCC (at donor H&P) 2 Х Х Х LDLT vs. non-LDLT) HCC (at transplant) Х Х Х LDLT vs. DDLT 3 Regeneration Х Х 4 Х Х Х Rejection 5 х Х Repository Х Х Х Х

286

288

289

290

287 Potential recipients with an evaluated donor must fulfill all of the following criteria:

• Potential recipient listed for single organ (liver) transplantation

- Patient is eligible for LDLT
- Age  $\geq$  18 years old at the time of donor history and physical exam
- Potential donor scheduled for evaluation (history and physical examination)
   within four weeks at the transplant center (this criteria is waived for subjects with
   HCV who are enrolling in the A2ALL LADR substudy. These subjects must
   have an identified donor who has passed telephone screening but may not have
   made an appointment)
- Informed consent obtained.
- 297

298	Patients with hepatitis C must fulfill all of the following criteria:
299	• Chronic hepatitis C virus infection and cirrhosis (may have concurrent HCC)
300	• HCV RNA positive (by qualitative or quantitative assay by local laboratory) pre-
301	transplantation (within 6 months of transplant if not on treatment or within 2
302	weeks if on treatment)
303	• If subject joins study after transplant; subjects who are receiving treatment for
304	HCV will be excluded from protocol biopsies.
305	• Informed consent obtained.
306	
307	Patients with HCC must fulfill all of the following criteria:
308	Diagnosis of hepatocellular carcinoma
309	• May have concomitant hepatitis C
310	Informed consent obtained.
311	
312	Contemporaneous DDLT controls must fulfill all of the following criteria:
313	• Potential recipient listed for single organ (liver) transplantation
314	• Age $\geq 18$ years old at transplant
315	Informed consent obtained.
316	
317	Donor candidates and donor control candidates must fulfill all of the following criteria:
318	• Meet donor criteria of the transplant center
319	• Age >= 18 years old at donation
320	• Be evaluated with a history and physical examination at the transplant center
321	• Donor controls must have good health, or mild to moderate medical conditions

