#### **4.6.1. Study Methods**

1294 This is a prospective cohort study which will collect data elements specific to a subset of 1295 patients enrolled in the A2ALL Cohort Study, who carry a diagnosis of cirrhosis and 1296 hepatocellular carcinoma. This cohort will include all LDLT recipients who consent to 1297 enrollment, have cirrhosis, and carry a diagnosis of hepatocellular carcinoma, or develop 1298 hepatocellular carcinoma while waiting for transplant. To address the Primary Aims and 1299 utilization of ablation, patients who undergo LDLT procedures (LDLT GROUP) will be 1300 compared with recipients who were enrolled but ultimately could not undergo a live 1301 donor transplant secondary to recipient or donor factors, and remained on the waiting list 1302 or eventually underwent deceased donor liver transplant (DDLT GROUP).

1303

1304 Since there will be a period of time before a suitable number of DDLT GROUP patients 1305 accumulate, a third group consisting of contemporaneous deceased donor controls will 1306 also be recruited (**CONTEMP GROUP**). These patients carry a diagnosis of cirrhosis 1307 and hepatocellular carcinoma, will be selected by the Data Coordinating Center, and 1308 enrolled at the time of transplant. This CONTEMP GROUP will serve as a control to 1309 address the question of operative and post-operative complication rates. It is anticipated that the CONTEMP GROUP will only be needed for the first two years of the study, 1310 1311 depending on number of patients enrolled.

- 1312
- 1313 A schematic for patient flow through the study is below.
- 1314

1315 1316 1317 1318 1319 1320	A2ALI	ents are enrolled in the study multiple data elements will be collected as part of the L Cohort Study. Specific data elements related to the subset of patients with cellular carcinoma, as well as their management while on the list is outlined below.
1321	1.	All enrolled patients with a confirmed or suspected diagnosis of HCC will first
1322		undergo evaluation to exclude metastatic disease and/or vascular invasion (chest
1323		CT, bone scan and abdominal MRI or contrast CT). These staging modalities and
1324		results will be recorded at 3-month intervals as required by UNOS.
1325	2.	All enrolled patients, who will wait > 3 months for transplant, will then undergo
1326		ablation of each lesion(s) with whatever technique(s) are currently utilized at each
1327		of the individual centers participating in this study (RFA, cryotherapy, alcohol

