1363	diagnosis of recurrence. An elevated AFP in the absence of a documented lesion
1364	on imaging will not be accepted as evidence of recurrence.
1365	
1366	Primary endpoints will be patient survival, cancer-free patient survival.
1367	
1368	Secondary endpoints will include loss of candidacy while on list due to tumor
1369	progression, overall use of ablative therapies, complications of ablative therapies,
1370	accuracy of preoperative imaging modalities, surgical and postoperative complication
1371	rates.
1372	
1373	4.6.2. Participant Selection
1374	See Section 4. for overall eligibility criteria, and Section 4.2.2 for further details on
1375	selection of contemporaneous controls. The specific inclusion and exclusion criteria for
1376	patients with HCC are given below.
1377	
1378	Inclusion Criteria:
1379	
1200	

- 1. Suspected or confirmed HCC which meet the UNOS definition for being listed 1380 for Stage I or Stage II priority. 1381 1382
  - a. A single mass lesion on imaging studies < 5 cm in diameter

1383	b. Multiple lesions on imaging studies, but no greater than three lesions and
1384	no single lesion $> 3$ cm.
1385	c. A tissue diagnosis of HCC.
1386	d. An AFP greater than $> 500$ ng/ml.
1387	2. Patients with greater than Stage II disease will also be enrolled, as long as they
1388	were accepted by the individual transplant center as acceptable for liver
1389	transplant.
1390	3. Patients with history of ablation prior to listing will also be eligible, as long as
1391	one of the features in section 1 above was present prior to the ablative procedure.
1392	
1393	Exclusion criteria :
1394	
1395	1. Evidence of metastatic disease based upon chest CT, bone scan and abdominal
1396	MRI or contrast CT.
1397	2. No tumor found in explant and no history of prior ablative therapy.
1398	3. Patients with synchronous cholangiocarcinoma.
1399	
1400	4.6.3. Data Elements
1401	In addition to the data elements collected for the A2ALL Cohort study, specific data
1402	elements will be collected in these patients with HCC. These include:
1403	Detential Desiniants resitive for UCC
1404	Potential Recipients positive for HCC
1405	
 
HCC data at Listing
 
HCC data at Enrollment
 

1406 1407	2. HCC data at Enrollment
1407	Desirients positive for UCC
1408	Recipients positive for HCC 1. HCC Data Immediately Prior to Transplant
1409	
 
ACC Data Infinediately Flor to Transplant
 
ACC Explant Assessment
 

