1410	
 
A HCC Explaint Assessment
 
HCC Post-operative Recurrence and Treatment Data
 

1411	5. Thee Post-operative Recurrence and Treatment Data
1412	
1413	4.6.4. Sample Size and Power Calculations
1414	It is anticipated (based on 1998-2002 data and trends) that approximately 75 patients
1415	(25% of all 300 LDLTs) will have undergone LDLT for HCC over the three-year period
1416	of the Retrospective study at the A2ALL study centers. Similarly, there should be
1417	approximately 125 patients (25% of all 500 non-LDLT) in the non-LDLT group to serve
1418	as controls. In addition, approximately 15% of Cohort patients are estimated to have
1419	HCC (0.15*360=) 54 LDLT and (0.15*710=) 106 non-LDLT. Thus, the total cohort for
1420	endpoints collected in both Retro and Cohort studies will be (75+54=) 129 LDLT and
1421	(125+106=) 231 non-LDLT. With this number of patients, there will be an 95% power to
1422	detect a 20% difference (e.g., 40% versus 60%) in recurrence of HCC (loss of transplant
1423	candidacy or post-transplant recurrence) between the LDLT group and non-LDLT group.

- 1424 These numbers should also allow for adequate comparison of patient survival, since
  - 1425 tumor recurrence typically leads to patient death.
  - 1426
  - 1427 The lowest power will be available for comparisons between LDLT and DDLT among
  - 1428Cohort patients only: an estimated 54 LDLT and 54 DDLT. For these comparisons,
Revised Cohort Protocol 031006Page 34 of 56

continuous outcomes will have more power than dichotomous outcomes. We will have 1429

1430 87% power to detect an effect size (number of standard deviations different) of 0.60

1431 between groups. Cohen considers and effect size of 0.50 to be moderate, and 0.90 to be 1432 large.

1433

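### Sections 4.6.4 and 4.6.5 define the HCC outcome for LDLT versus non-LDLT differently, and the undefined *presence* of tumor in 4.6.5 can count unchanged entry tumors as events, mainly in the non-LDLT group

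*Protocol*

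**What the plan says.** Section 4 makes "Diagnosis of hepatocellular carcinoma" an entry criterion for HCC patients, and 4.6.2 accepts suspected or confirmed disease. Under 4.6.1, LDLT recipients are compared with enrolled patients who could not have a live "donor transplant secondary to recipient or donor factors, and remained on the waiting list" or later received a deceased donor liver. The comparator therefore mixes transplanted and untransplanted patients.

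Two sections then describe the outcome of this comparison:

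- Section 4.6.4 claims 95% power to "detect a 20% difference (e.g., 40% versus 60%) in recurrence of HCC (loss of transplant" "candidacy or post-transplant recurrence) between the LDLT group and non-LDLT group".
- Section 4.6.5 plans: "The difference between recurrence (or presence) proportions for LDLT versus" "non-LDLT patients will also be estimated using a 95% confidence interval".

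The word *presence* is not defined, has no time point and is not assigned to either group. The only window nearby is one year, and it belongs to a separate descriptive item: the proportion of "HCC recurring within one year will be presented, with 95% CI".

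Section 4.6.1 also states: "Primary endpoints will be patient survival, cancer-free patient survival". It lists loss of candidacy through tumor progression as a secondary endpoint.

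**The concern.** One contrast has two outcome definitions, and the one to be analysed is not the one that was powered.

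The added word matters because tumor is what qualifies a patient for this aim. Once the native liver is out, tumor found in a recipient is recurrence. In a patient still waiting, tumor found on imaging may simply be the lesion that brought the patient into the study. An untransplanted patient cannot have post-transplant recurrence, so *presence* reads most naturally as the substitute event for such patients. On that reading, a waiting patient with an unchanged lesion, still eligible for transplant, counts as a failure. The contrast would then partly measure who has been transplanted rather than what LDLT does to the cancer.

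Reading the word as tumor at any time from entry, in both groups, does not help. Nearly everyone would then be an event and the contrast would carry no information.

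Comparative HCC recurrence is a primary objective of this aim (section 3.6), so the definition should not be left to interpretation.

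**Working it through.** **Inputs**

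- LDLT patients (4.6.4): 75 + 54 = 129. Non-LDLT patients: 125 + 106 = 231.
- Design difference (4.6.4): 40% versus 60%, with stated power 95%.
- Two-sided alpha 0.05. Section 4.6.4 gives no alpha, so this is taken from the 95% interval in 4.6.5.
- Assumptions, because the protocol gives no values: r, the true rate of the 4.6.4 event, equal in both groups; w, the share of event-free non-LDLT patients still waiting; q, the share of those scored as having tumor present.

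**1. The plan's own figure**

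Power = Φ[(|p₁ − p₂| − 1.96·SE₀)/SE₁], where SE₀ is the pooled standard error under the null and SE₁ the unpooled one.

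The pooled proportion is (129 × 0.40 + 231 × 0.60)/360 = 0.528, so SE₀ = 0.0549 and SE₁ = 0.0538.

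Power = Φ[(0.20 − 1.96 × 0.0549)/0.0538] = Φ(1.72) = 0.957. With a continuity correction it is 0.950. The stated 95% is right for the 4.6.4 event.

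**2. What presence adds when LDLT has no effect**

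LDLT proportion = r. Non-LDLT proportion = r + (1 − r)·w·q. The spurious difference is (1 − r)·w·q.

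Example with r = 0.20, w = 0.20, q = 1: the non-LDLT proportion is 0.20 + 0.80 × 0.20 = 0.36, a difference of 16 points. The pooled proportion is 0.303, SE₀ = 0.0505 and SE₁ = 0.0473. The chance of a significant result favoring LDLT is Φ[(0.16 − 1.96 × 0.0505)/0.0473] = Φ(1.29) = 0.90.

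| r | w | q = 1 (all scored present) | q = 0.5 (half tumor-free) |
|---|---|---|---|
| 0.20 | 0.20 | 16 points, 0.902 | 8 points, 0.385 |
| 0.20 | 0.30 | 24 points, 0.998 | 12 points, 0.693 |
| 0.40 | 0.20 | 12 points, 0.590 | 6 points, 0.193 |
| 0.40 | 0.30 | 18 points, 0.910 | 9 points, 0.375 |

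With q = 1, classification alone produces the 20-point design difference at w = 0.20/0.80 = 0.25 (r = 0.20) or w = 0.20/0.60 = 0.33 (r = 0.40).

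**3. Is a waiting share of 20 to 30% plausible?**

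Section 4.6.4 expects 106 non-LDLT HCC patients in the Cohort Study and 54 DDLT. If all 54 come from the 106, then 52/106 = 49% are never transplanted. This is a rough guide, not an estimate of w. Some of the 52 will have died or lost candidacy, and some of the 54 may be contemporaneous controls from outside the 106.

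**The case against.** **The text does not assign presence to controls.** Grammatically the word covers both groups, and a definition may exist in an analysis plan that is not at hand. This stands in part: how the word would be applied is an interpretation. The mismatch between 4.6.4 and 4.6.5 is on the page either way.

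**A reader might infer that every waiting control is an event by definition.** The protocol does not support that. Under 4.6.1, patients expected to wait more than 3 months have their lesions ablated and are imaged every 3 months, and local recurrence while waiting is recognised as an event of its own. Section 4.6.2 also admits suspected HCC and patients ablated before listing. A waiting patient can therefore have no detectable tumor, which is why q = 1 is the extreme case.

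**A reader might extend the criticism to cancer-free survival.** That is weak. Section 3.6 frames disease-free survival among patients who undergo LDLT or DDLT. The population table in section 4 separates HCC at donor evaluation from HCC at transplant. Section 4.6.5 does not say that cancer-free survival is judged by tumor presence. The DDLT GROUP label in 4.6.1, which also takes in waiting patients, blurs this enough to justify one clarifying sentence.

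**The affected item is modest.** It is one interval estimate in a secondary aim, under analysis introduced as mainly descriptive, and is not a named primary endpoint. This stands and lowers the severity. It does not remove the conflict, because 4.6.4 claims 95% power for this contrast.

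**Conclusion.** The point holds as an inconsistency with a predictable direction of bias, and should be fixed. The two sections give different events for the same comparison, and the undefined term in 4.6.5 would favor LDLT if it is scored as it most naturally reads. The 95% power is correct for the 4.6.4 event and does not carry over to recurrence or presence.

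The size is uncertain. With 20% of event-free controls waiting, the spurious difference runs from 6 to 16 points across true rates of 20% and 40% and across all or half of waiting patients scored present. The matching chance of a significant result runs from 19% to 90%. These figures illustrate the risk and are not estimates, because the protocol gives no value for the true rate, the waiting share or the share scored present.

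It would also be wrong to conclude that the 4.6.4 event is unbiased once adopted. Patients grouped by having received LDLT cannot have lost candidacy before it, so simple grouping by receipt still favors LDLT.

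**What to change.** 1. In 4.6.5, delete *(or presence)*, or define it as new or progressive tumor after entry.
2. Use one event in 4.6.4 and 4.6.5 for both groups: loss of candidacy due to tumor progression, or documented post-transplant recurrence.
3. Count that event from donor evaluation, with LDLT as a time-dependent covariate as already planned in 4.1.5, so that waiting time before LDLT is not credited to the LDLT group.
4. State that cancer-free survival applies to the LDLT versus DDLT comparison from transplant, in line with section 3.6.

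The cost is mostly wording. The 95% in 4.6.4 is a two-proportion figure, so it should be restated if the comparison becomes time-to-event. The apparent LDLT benefit may shrink. It must also be confirmed that both components of the event are available for the Retrospective Study patients, who supply 75 + 125 = 200 of the 360 subjects; the protocol does not show what was recorded for them.

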#### 4.7. Secondary Aim 3: To systematically characterize liver regeneration and function in donors and recipients.

1454 Information about liver regeneration after liver transplantation remains descriptive and is 1455 limited by our inability to directly sample liver tissue in the days after liver surgery. 1456 Following donation and transplantation, it has been observed that hepatic function of 1457 living liver donors returns to normal soon after right hepatic lobe resection using standard 1458 serum tests of liver function. Recipients of living donor liver transplants also have rapid 1459 return of function, however there may be a reduction and delay in recovery of hepatic 1460 metabolism following LDLT compared to whole DDLT, which has been observed with 1461 respect to the metabolism of immunosuppressive compounds.

1462

1463 Regeneration may fail if the graft is excessively small or damaged in other ways though 1464 the factors associated with graft function have not been adequately studied. Finally, it 1465 remains uncertain when and if the liver volume returns to its baseline following this 1466 procedure.

1467

1468 Initiation of molecular pathways associated with liver regeneration previously identified

1469 in rodent models is presumably necessary for hepatic recovery in the human living donor

- 1470 liver transplant setting in both donors and recipients. It is presumed that failure of
- 1471 regeneration is a consequence of a failure to initiate these events though limitations in our
- 1472 ability to directly assess liver tissue over time has prevented confirmation of these expectations.
- 1473

1475 Primary Objectives

14/5	Primary Objectives
1476	• To measure hepatic function and mass in living donors at study entry,
1477	perioperatively, and following hepatectomy, and determine whether return of
1478	hepatic function following donation correlates with rate of liver regeneration,
1479	biochemical impairment, and clinical events, and if return of function is complete
1480	by 3-6 months post-resection.
1481	• To correlate liver function in donors with long-term health outcomes and the
1482	incidence of clinical complications.
1483	
 
To correlate success or failure of regeneration with a series of selected clinical
 

1484	and laboratory variables in donors and recipients
1485	
 
To collect liver biopsy and serum samples prospectively from a large series of
 

1485	donors and recipients which may form the basis for subsequent characterization of
1480	protein and gene expression of selected inflammatory and growth-related
1487	molecules.
1489	molecules.
1409	
1490	4.7.1. Study Methods
	Tirrit Study Methous
1491	A Destaution of linear many and for stient
1492	A. Restoration of liver mass and function:
1493	
1494	In this cohort we will limit our observations of restoration of liver mass to measurement
1495	of liver volume at defined interval after transplantation and donation and clinical and
1496	standard laboratory assessment at standardized intervals.
1497	D. Tianus and communications
1498	B. Tissue and serum collection:
1499	
1500	Tissue and sera will be collected and stored prospectively for eventual analysis using
1501	molecular and proteomic techniques to detect selected molecules associated with
1502	regeneration and repair.
1503	Liver bionging will be collected prior to bonotoctomy in the living denorging the book
1504 1505	Liver biopsies will be collected prior to hepatectomy in the living donors, on the back-
	table, and after reperfusion of the liver graft in recipients. These will be processed and
1506 1507	stored for eventual analysis. In addition, sera will be collected and stored at defined intervals from donor and recipients which will be available for subsequent studies of gene
1507	and protein expression.
1508	and protein expression.
1509	a. Tissue samples
1510	a. Tissue samples
1512	i) In the living donor setting, one Tru-cut core biopsy of the right lobe of the donor liver
1513	will be performed prior to the removal of the right lobe (control in situ biopsy), and one
1514	on the back table after flushing with preservation solution (cold ischemia biopsy), for
1515	baseline assessment. Approximately 30-60 minutes after reperfusion of the right lobe into
1516	the recipient, the donated portion of the liver will also have one Tru-cut core biopsy
1517	performed (post-reperfusion biopsy). All biopsy specimens will be split in the operating
1518	room, with two-thirds placed in RNAlater to be processed for RNA or immunohistology,
1519	and one-third placed in paraffin block for later section/H&E histology.
1520	1 1
•	

1521 ii) In the DDLT donor setting, biopsies will be obtained from the donor liver on the back

table (cold ischemia biopsy), and then approximately 30-60 minutes after implantation

1523 (post-reperfusion biopsy), as described above. The control DDLT arm is important for

1524 comparison and correlation of molecular events with ischemic injury and/or graft to 1525 recipient size ratio.

- 1526
- 1520 1527 S

Serum samples will be obtained at baseline (preoperatively), intraoperatively prior toresection or transplantation and at the time of final biopsy, on post-operative days (PODs)

1529 1 and 7, and at 2, 4, 12 and 24 weeks.

